## 1. Overview of analyses

This document contains the statistical analysis plan for ‘Evaluating scanning competence following a structured POCUS training program for general practitioners: A hybrid effectiveness-implementation study’. The aim is to clarify the intended analyses prior to collection of the primary outcome. This document describes the analyses to be performed in the main study paper.

The main time points for analyses are at baseline, after three months (at the end of the educational intervention) and after six months.

Participants will be recruited on the first teaching seminar on the 3rd of March 2022 (baseline). Effectiveness related outcomes will be collected on the third teaching seminar on the 9th of June 2022 (three months after baseline) and on the 7th and 8th of September 2022 (six months after baseline). Implementation related outcomes will be collected from baseline until the end of the trial on the 8th of September 2022 (six months after baseline).

## 2. Background of the trial

The trial is designed as a hybrid effectiveness-implementation study allowing for simultaneously evaluating the effect of a training program in real world settings and evaluating the implementation strategy (1). The trial is categorized as a type 1 hybrid design (2) with the purpose to rigorously test participants’ competences when finishing an ultrasound course and again after three months evaluate if participants maintain their competences. Secondly, we gather implementation data about the uptake of scanning procedures in practice and adherence to the training program (2).

The principal research aim is to evaluate ultrasound competences after an educational intervention by use of the OSAUS score. The study is conducted in Danish general practice and the study is registered at ClinicalTrials.gov (registration number: NCT05274581).

### 2.1. Eligibility

#### 2.1.1. Inclusion criteria

To be eligible for the study, subjects must fulfill the following criteria:

1. GP, i.e., be a postgraduate medical doctor with a specialization in general practice.
2. Work in office-based general practice in Denmark
3. Have access to an ultrasound device in the practice during the study period

#### 2.1.2. Exclusion criteria

To be eligible for this study, subjects must not meet any of the following criteria:

1. GPs with a possible conflict of interest (e.g., industry affiliation related to the use of ultrasound)
2. No signed informed consent to participate.

### 3. Adherence

Teachers at the educational intervention will support adherence to research protocols. The teacher will act as mentors for the participants and monitor participants' activity on the online platform. The teachers will reach out to participants who fail to register data and reminders are sent to the participants to remind about registering of all performed POCUS examinations during clinical work.

### 4. Baseline characteristics

Tables of summary statistics will be produced in one group. The table will include:

Variable	Unit	Description
Age	years	mean(SD) and median(IQR)
Sex	male, female, other	frequency (%)
Experience as a medical doctor	years	mean(SD) and median(IQR)
Experience as a GP	years	mean(SD) and median(IQR)
Experience with POCUS	years	mean(SD) and median(IQR)
Previous POCUS training	course participation, training during residency, experience from employment within another medical specialty, ad hoc training by colleague, other, no previous training	frequency (%)
Type of practice	solo-practice, partnership practice, solo-practice in collaboration, partnership practice in collaboration, other	frequency (%)
Location of practice	rural, city, mixed	frequency (%)
Distance to radiology department	km	mean(SD) and median(IQR)
Region	North Denmark Region, Central Denmark Region, Region of Southern Denmark, Region Zealand, Capital Region of Denmark	frequency (%)

Number of full-time equivalent GPs working in the clinic	1-20	mean(SD) and median(IQR)
Number of patients listed with the clinic	1000-20000	mean(SD) and median(IQR)

*Note:* The number of missing for each variable will be reported.

## 5. Effectiveness outcomes

### 5.1. The primary effectiveness outcome

The primary outcome is the Objective Structured Assessment of Ultrasound Skills (OSAUS) score after three months (P1) and six months (P2).

The OSAUS assessment tool has been developed and validated as a generic tool for assessing scanning competence (3). The OSAUS scale consists of seven items: ‘indication for the examination’, ‘applied knowledge of ultrasound equipment’, ‘image optimization’, ‘systematic examination’, ‘interpretation of images’, ‘documentation of the examination’ and ‘medical decision-making’ and each item is rated using a provided five-point Likert-scale with descriptions of performance ranging from very poor (score = 1) to excellent (score = 5). Hence, for each scanning modality a total score from 7 to 35 points may be achieved.

(P1): The summarized OSAUS score after the educational period (three months after baseline) for all ten modalities will be calculated as percentage of maximum score. To summarize normal and non-normal data similarly mean(SD) as well as median(IQR) will be presented. Minimum and maximum score will also be presented.

(P2): The summarized OSAUS score after six months for all ten modalities will be calculated as percentage of maximum score and presented as mean(sd) and median(IQR). Minimum and maximum score will also be presented.

### 5.2 Secondary effectiveness outcome measurements

(S1). The total OSAUS score and the total items scores for each of the ten scanning modalities included in the curriculum after the educational period (three months after baseline) will be calculated and presented as mean(sd) and median(IQR). Minimum and maximum score will also be presented.

(S2). A OSAUS score between 2.5 and 3.0 has previously been found valid and reliable to distinguish between novice POCUS users and experts(4). To apply a conservative cut-off (3.0 for each item) yields a combined pass/fail score for a scanning modality of 21.0 points of a maximum of 35.0 points. We calculate the proportion of GPs, who achieve a minimum OSAUS score of three for all seven domains for each of the ten scanning modalities after the educational period (three months after baseline). As variation in scores can occur between the five expert assessors. We will normalize the scores by multiplying a given assessors score

with  $(0.2 \times \text{sum of scores of all five accessors} / \text{the given accessors score})$  prior to calculating the proportion of successful GPs.

(S3): We calculate the proportion of GPs, who achieve a minimum OSAUS score of three for all seven domains for each of the ten scanning modalities after six months.

(S4): Before the OSAUS assessment the GPs will be asked to assess whether or not they have scanning competence within the specific scanning modality to perform the scan un-supervised in general practice (yes to a very high degree, yes to a high degree, yes to some degree, yes to a lesser degree, no, unsure). We calculate the proportion of GPs, who rate themselves as competent to perform POCUS un-supervised in general practice, after the educational period (three months after baseline), within each of the ten scanning modalities.

(S5): We calculate the proportion of GPs, who rate themselves as competent to perform POCUS un-supervised in general practice, after six months, within each of the ten scanning modalities.

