Continuous medical education for GPs is centrally organized under the wings of the Danish Medical Association for General Practitioners (Praktiserende Lægers Organisation PLO-e). PLO-e is the practical organizer of the ultrasound course delivered in this educational intervention. The ultrasound course has been included in PLO-e's course catalogue for 2022 and as such all GPs working in Danish general practice has had the opportunity to sign-up for the course. Hence, PLO-e has handled the participant recruitment and registration as well as the financial and practical aspects of organizing and executing the course. PLO-e had no influence on the scientific content or data collection in the study.

The study will be coordinated from CAM AAU and data will be collected by the research team at the training sessions and by the participating general practitioners in their clinics. All study data will be stored at a secure server at Aalborg University.

10 Participants

Twenty GPs working in office-based general practice in Denmark, who have signed up for a PLO-e ultrasound course, will be invited to participate in the study. To participate a GPs must fulfill the inclusion criteria and not the exclusion criteria

Inclusion criteria:

1. GP, i.e., be a postgraduate medical doctor with a specialization in general practice.
2. Work in office-based general practice in Denmark
3. Have access to an ultrasound device in the practice during the study period

Exclusion criteria:

1. GPs with a possible conflict of interest (e.g., industry affiliation related to the use of ultrasound)
2. No signed informed consent to participate.

[figure not shown]
The educational intervention will be delivered by an educational team (UM, TL, BS, TMJ, NS, CS), who is an experienced GPs, POCUS users and teachers. The competence assessment (OSAUS score) will be delivered by a team of POCUS experts (SKA, OG, MBJ, CS and LP), who have extensive POCUS experience.

11a Description of the intervention

All participants will receive the educational intervention. The educational intervention consists of three teaching seminars over three months, a curriculum of 10 POCUS applications, an online learning platform providing educational support before, during and after the teaching sessions (see Figure 1).

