The primary outcome is the Objective Structured Assessment of Ultrasound Skills (OSAUS) score scored after three (P1) and six months (P2).

The OSAUS assessment tool has been developed and validated as a generic tool for assessing scanning competence¹³. The OSAUS scale consists of seven items: ‘indication for the examination’, ‘applied knowledge of ultrasound equipment’, ‘image optimization’, ‘systematic examination’, ‘interpretation of images’, ‘documentation of the examination’ and ‘medical decision-making’ and each item is rated using a provided five-point Likert-scale with descriptions of performance ranging from very poor (score = 1) to excellent (score = 5). All items are weighted equally, as high inter-item correlation have been found previously¹⁴. Hence, for each scanning modality a total score from 7 to 35 points may be achieved.

(P1): The summarized OSAUS score after the educational period (three months after baseline) for all ten modalities will be calculated as percentage of maximum score and presented as median, IQR, minimum and maximum score.

(P2): The summarized OSAUS score after six months for all ten modalities will be calculated as percentage of maximum score and presented as median, IQR, minimum and maximum score.

Secondary outcomes

(S1). The total OSAUS score and the total items scores for each scanning modality included in the curriculum after the educational period (three months after baseline) will be calculated and presented as median, IQR, minimum and maximum score.

(S2). We calculate the proportion of GPs, who achieve a minimum OSAUS score of three for all seven domains for each of the ten scanning modalities after the educational period (three months after baseline). As variation in scores can occur between the four expert assessors. We will normalize the scores by multiplying a given assessors score with $(0.2 \times \text{sum of scores of all five assessors} / \text{the given assessors mean score})$ prior to calculating the proportion of successful GPs.

(S3): We calculate the proportion of GPs, who achieve a minimum OSAUS score of three for all seven domains for each of the ten scanning modalities after six months.

(S4): We calculate the proportion of GPs, who rate themselves as competent to perform POCUS un-supervised in general practice, after the educational period (three months after baseline), within each of the ten scanning modalities.

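### The S2 normalisation in the SAP is wrong as written, and the formula evidently intended should not supply the main S2 figure

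*SAP*

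**What the plan says.** Both documents define S2 as the proportion of GPs reaching at least 3 in every one of the seven OSAUS items, for each of the ten modalities, at three months. Both apply a normalisation before the cut-off.

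- **SAP section 5.2 (S2):** "We will normalize the scores by multiplying a given assessors score" by 0.2 × "sum of scores of all five accessors" / "the given accessors score".
- **Protocol section 12 (S2):** the same constant and numerator ("sum of scores of all five assessors"), but the divisor is "the given assessors mean score".

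Neither document says whether the summed scores are raw ratings, totals or means, or what an assessor's mean is averaged over. The protocol leads into the formula with "As variation in scores can occur between the four expert assessors" and then sums over five. The SAP says five throughout S2, and protocol section 10 lists five people after "The competence assessment (OSAUS score) will be delivered by a team of POCUS experts".

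SAP section 7 has each assessor rate four participants. S3, the six-month counterpart of S2, has no stated normalisation in either document. The only SAP amendment (section 13) concerns S7.

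**The concern.** In the SAP the thing multiplied and the divisor carry the same name, so the rule as printed does not normalise. It replaces each GP's rating by a quantity that cannot tell one GP from another at the cut-off. The protocol has a different divisor and nothing explains the change, so a programmer has to choose a repair.

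The adjustment comes before a hard threshold, so the choice decides the reported proportion. There is a further question once the wording is repaired: whether rescaling integer ratings and then requiring at least 3 on all seven items gives a fair pass rate. Finally, if S2 is rescaled and S3 is not, the three- and six-month proportions are on different scales for anyone who reads them together.

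**Working it through.** **Figures in the plan.** Five assessors give 1/5 = 0.2, the stated constant (four would give 0.25). 5 assessors × 4 GPs = 20 GPs. 7 items × 3 = 21, the SAP's combined pass score. These agree with one another.

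**SAP formula, taken literally.** Let s be a GP's rating on one item of one modality. Then s × (0.2 × Sum / s) = 0.2 × Sum. The result depends on what Sum contains:

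1. *Raw ratings of all GPs on that item and modality.* The lowest possible value is 0.2 × 20 × 1 = 4.0, or 0.2 × 16 × 1 = 3.2 with the 16 GPs expected in SAP section 8. Everyone passes, even if every rating is 1.
2. *The five assessors' means on that item and modality.* Every GP gets the same value, so a modality is passed by all or by none. Example (assumed): means 2.50, 2.75, 2.75, 3.00, 3.25 sum to 14.25, and 0.2 × 14.25 = 2.85. Everyone fails.
3. *All assessors' ratings of the same GP.* With each assessor rating four of 20 GPs, only one rating exists. The result is 0.2 × s, at most 0.2 × 5 = 1.0. Nobody passes.

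**Protocol formula.** Assume assessor means 3.00, 3.25, 3.50, 3.75, 4.00, each attainable from four integer ratings.

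- *Sum read as the sum of the five means:* 0.2 × 17.5 = 3.5.

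| Assessor mean | Factor (3.5 / mean) | Raw 3 becomes |
|---|---|---|
| 3.00 | 1.167 | 3.50 |
| 3.25 | 1.077 | 3.23 |
| 3.50 | 1.000 | 3.00 |
| 3.75 | 0.933 | 2.80 |
| 4.00 | 0.875 | 2.63 |

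- *Sum read as raw ratings, four GPs per assessor:* 12 + 13 + 14 + 15 + 16 = 70, and 0.2 × 70 = 14. Factors run from 14/3.00 = 4.67 to 14/4.00 = 3.50, so a raw 1 passes. Restoring the word mean in the divisor alone therefore does not fix the text.

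**Behaviour of the sensible version at the cut-off.** A factor just below 1 is enough to fail a raw 3. A factor must reach 3/2 = 1.5 to rescue a raw 2, well above the 1.167 in the table. The adjustment therefore mostly removes passes, and a GP needs all seven items.

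A simulation shows the size. All inputs are assumed: 600 runs, 20 GPs, four allocated at random to each of five assessors, ten modalities, seven items, ratings rounded and limited to 1–5, SDs of 0.2 (GP), 0.3 (GP by modality) and 0.6 (item), and overall assessor means.

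| Latent mean | Assessor shifts | Unbiased S2 | Unnormalised S2 | Mean-based S2 |
|---|---|---|---|---|
| 3.6 | none | 71.6% | 71.6% | 38.1% |
| 3.6 | −0.5 to +0.5 | 71.6% | 67.8% | 35.9% |
| 4.0 | none | 90.5% | 90.5% | 60.5% |
| 4.0 | −0.5 to +0.5 | 90.8% | 86.3% | 62.9% |

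With no strictness difference the formula nearly halves S2 at the lower latent mean. With real differences, the unnormalised figure is about 4 points from the unbiased value at both latent means. The normalised one is about 36 points away (71.6 − 35.9) and 28 points away (90.8 − 62.9).

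**The case against.** The strongest reply is that this is a dropped word. Both documents say the purpose is to allow for variation between assessors, 0.2 is 1/5, and the protocol supplies the mean. Together these make the average of the five assessors' means over the assessor's own mean the evident intent, and a factor near 4 on a 1–5 scale is not a normalisation anyone would want. This stands. A reader might infer that S2 cannot be reconstructed from either document, or that every GP would pass under the SAP. The first is too strong for the protocol. The second ignores the readings in which a whole modality fails or nobody passes.

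The averaging level is unstated but seems to matter little. In a separate simulation (assumed latent mean 3.8, shifts −0.5 to +0.5), S2 was 0.554 with overall means, 0.556 per modality and 0.565 per modality and item.

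The protocol's count of four might suggest that 0.2 is the wrong constant. The SAP and the protocol's own list both give five, so four looks like a slip.

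The S2–S3 mismatch should not be overstated either. No comparison of the two is planned. Maintenance of competence is addressed by P1, P2 and S6.

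What survives is that the governing SAP sentence is wrong as printed, the repair must be inferred, and the inferred repair behaves badly at the cut-off.

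**Conclusion.** The SAP rule is wrong as written: it reduces to 0.2 × sum and cannot separate GPs. The protocol points to the intended factor but does not say that the sum is of means or at what level they are taken. Applied as evidently intended, the factor fails every raw 3 from an assessor whose mean exceeds the average of the five.

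The algebra and the behaviour at the cut-off follow from the documents alone. The percentages (for example 71.6% to 38.1%) rest on assumed means and SDs and illustrate size only; they are not predictions for this trial.

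The reach is limited to S2, which is descriptive and untested. It would be wrong to infer that the primary results are affected: P1, P2, S1, S3 and S6 have no stated normalisation. It should be fixed because the correction is cheap and the choice of reading can move S2 anywhere from 0% to 100%.

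**What to change.** By a dated SAP amendment:

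1. Correct the factor to (mean of the five assessors' mean scores) / (the given assessor's mean score) and state the averaging level. An overall mean rests on up to 4 × 10 × 7 = 280 ratings per assessor; a mean per item and modality rests on 4. SAP section 13 shows that analysis had begun, so also record the formula actually run if it differs.
2. Report S2 on unnormalised scores, the scale on which S3 is defined, as the main figure. Show the normalised S2 as a sensitivity result.
3. Reconcile the four assessors in protocol section 12 with the five given there, in protocol section 10 and in SAP section 5.2.

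The cost is one corrected sentence and one extra table, with no new data. The downside is that the unnormalised figure leaves any real difference in assessor strictness in place, which is why the normalised result should still be shown.

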Key secondary outcomes	
Secondary outcome 1 (S1): For GPs, participating in a POCUS training program with online support and three teaching sessions, the OSAUS scores and the item scores, after the educational period (three months after baseline), for each of the ten scanning modalities included in the curriculum.
 
Secondary outcome 2 (S2): The proportion of GPs, participating in a POCUS training program with online support and three teaching sessions, who have an ultrasound competence score (OSAUS score) of three or above after the educational period (three months after baseline), for all of the seven OSAUS items of each of the ten scanning modalities included in the curriculum.
 
Secondary outcome 3 (S3): The proportion of GPs, participating in a POCUS training program with online support and three teaching sessions, who have an ultrasound competence score (OSAUS score) of three or above six months after baseline, for each of the ten scanning modalities included in the curriculum.
 
Secondary outcome 4 (S4): The proportion of GPs, participating in a POCUS training program with online support and three teaching sessions, who rate themselves to be competent to perform un-supervised POCUS in general practice, after the educational period (three months after baseline), for each of the ten scanning modalities included in the curriculum.
 
Secondary outcome 5 (S5): The proportion of GPs, participating in a POCUS training program with online support and three teaching sessions, who rate themselves to be competent to perform un-supervised POCUS in general practice, six months after baseline, for each of the ten scanning modalities included in the curriculum.
 
Process-related outcome 1 (PR1): The number of performed POCUS examinations by each GP in the first six months after introducing POCUS use in general practice (months 1-6 after baseline).
 
Process-related outcome 2 (PR2): The number of adverse events and near-miss cases associated with the use of POCUS reported by the participating GPs in the first six months after introducing POCUS use in general practice (months 1-6 after baseline).
 
Process-related outcome 3 (PR3): The proportion of GPs, participating in a POCUS training program with online support and three teaching sessions, who have completed the different educational elements in the educational intervention three months after baseline.

3 Protocol version

Version 9. Marts 2nd 2022

4 Funding

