### 5.3 Additional outcomes (not predefined in study protocol)

(S6): Change in OSAUS scores between 3 and 6 months are calculated using linear regression. Scores after 3 and 6 month will be compared by a paired t-test.

(S7) we will use a linear regression model to test associations between OSAUS score at 3 and 6 months and the following variables: experience as a GP (years), experience using POCUS (years), participation in the planned course activities (number of completed webinars and course days), number of completed pre-post quizzes, number of completed assignments, number of performed POCUS examinations.

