## 7. Data collection

### *The OSAUS score*

The participants will step-a-side to have their scanning competence assessed by a POCUS-expert assessor, who is blinded to the participants prior experience with POCUS, the number of performed POCUS examinations, and any other elements in the participants' learning process. Each POCUS-expert assessor will rate four participants twice: three months after baseline and six months after baseline. The POCUS-expert assessor will rate the individual participants screening competences by asking the below questions (blinded to the participants prior experience with POCUS, the number of performed POCUS examinations, and any other elements in the participants' learning process):

- 1) In which clinical scenarios would you perform this POCUS examination (Item 1 in the OSAUS)

The POCUS-expert assessor will then ask participants to demonstrate the POCUS examination (for maximum five minutes) to rate the following:

- 2) Applied knowledge of the ultrasound equipment (Item 2 in the OSAUS)
- 3) Image optimization (Item 3 in the OSAUS)
- 4) Systematic examination (Item 4 in the OSAUS)
- 5) Interpretation of images (Item 5 in the OSAUS)

Following the demonstration of the scan, the POCUS-expert assessor will present the participants with one picture of common pathology and ask the participants the following questions:

- 6) How would you interpret these ultrasound findings? (Item 6 in the OSAUS)
- 7) If you were to describe this examination in the medical record, what would you write? (Item 6 in the OSAUS)
- 8) What would you do if you found it? (Item 7 in the OSAUS)

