### 13. SAP Amendment

During the data analysis it was decided to drop the additional outcome S7, as this analysis did not add information to the results of the study beyond what was reported for the predefined outcome PR3.

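### S2 (three months) is rescaled by assessor but S3 (six months) is not, and the rescaling itself pushes the pass proportion down

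*SAP*

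**What the plan says.** Protocol 12 and SAP 5.2 define S2 as the proportion of GPs, per modality, scoring at least 3 on all seven OSAUS items at three months. Both add an assessor adjustment to this outcome. The protocol puts it as "We will normalize the scores by multiplying a given assessors score with" a factor, and the SAP applies it "prior to calculating the proportion of successful GPs". The factor is 0.2 times the sum over five assessors, divided by the assessor's mean score (protocol) or by the assessor's score (SAP).

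S3 follows in both documents with the same cut and no adjustment. The SAP wording is "S3): We calculate the proportion of GPs, who achieve a minimum OSAUS score of three for all seven domains", at six months. SAP 10 does not extend the adjustment to S3.

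Five further passages bear on this:
- SAP 7: "Each POCUS-expert assessor will rate four participants twice: three months after baseline and six months after baseline".
- SAP 5.3 (S6): "Scores after 3 and 6 month will be compared by a paired t-test", with no normalisation stated. SAP 5.1 states none for P1 and P2.
- SAP 5.2 says that a cut of 3.0 per item "yields a combined pass/fail score for a scanning modality of 21.0 points of a maximum of 35.0 points".
- The registration table in Protocol 2b gives S3 as a score "OSAUS score) of three or above six months after baseline", without the all-seven condition that Protocol 7, Protocol 12 and SAP 5.2 keep.
- Protocol 12 speaks of four expert assessors in the sentence before a formula built for five.

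**The concern.** Protocol 7 asks whether competence is reached at three months and then maintained at six. S2 and S3 express that as the share of GPs reaching the expert-rated cut, so readers will set them side by side. If one is rescaled and the other is not, they can differ with no change in skill.

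There is a second problem inside S2. Item scores are whole numbers and the cut lies exactly on one of them. A multiplicative factor just below 1 moves every 3 under the cut, while a factor just above 1 brings no 2 up to it. The adjustment is meant to even out severe and lenient assessors, but at this threshold it can remove passes without restoring any.

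**Working it through.** **The plan's own figures.** 7 × 3 = 21 and 7 × 5 = 35, as SAP 5.2 states. 0.8 × 20 = 16 GPs and 16 × 10 = 160 questionnaires, as SAP 8 states. Five assessors × 4 GPs = 20.

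**The factor.** For assessor j with mean item score m_j, the workable reading of the protocol is f_j = 0.2 × (m_1 + … + m_5) / m_j. If the sum were taken over all 16 × 10 × 7 = 1120 item scores at a mean of 3.6, the factor would be 0.2 × 1120 × 3.6 / 3.6 = 224 and everyone would pass. Under the SAP's denominator, score × (0.2 × sum / score) = 0.2 × sum. Every rating then takes one common value, so S2 is 0% or 100%.

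**Effect at the cut of 3 (protocol factor).**
- A raw 3 passes only if 3f ≥ 3, so it fails for any f < 1.
- A raw 2 passes only if 2f ≥ 3, so it needs f ≥ 1.5. The assessor's mean would have to be at or below two-thirds of the five-assessor average.
- A raw 4 passes if f ≥ 0.75.

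While every factor stays below 1.5, normalised S2 cannot exceed raw S2.

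**Worked example (assumed assessor means).** The average is 0.2 × (3.70 + 3.75 + 3.80 + 3.85 + 3.90) = 3.80.

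| Assessor mean | f | Raw 3 becomes |
|---|---|---|
| 3.70 | 1.027 | 3.08 |
| 3.75 | 1.013 | 3.04 |
| 3.80 | 1.000 | 3.00 |
| 3.85 | 0.987 | 2.96 |
| 3.90 | 0.974 | 2.92 |

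The eight GPs of the last two assessors now need a 4 on every item. A raw 2 would be rescued only for an assessor whose mean is at most 3.80 / 1.5 = 2.53.

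**Size (simulation; all distributions assumed).** Item score = mean + assessor + GP + GP-by-modality + item error, rounded and held to 1–5. The layout is 5 assessors × 4 GPs × 10 modalities × 7 items. Assessor and GP effects are the same at both visits, so there is no true change. SDs are GP 0.4, GP-by-modality 0.4, item 0.5 and assessor 0 to 0.8, with 600 replicates per setting.

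| Mean item score | S2 normalised | S3 raw |
|---|---|---|
| 3.4 | 34–37% | 59–64% |
| 3.8 | 55–57% | 73–83% |
| 4.2 | 73–77% | 84–94% |
| 4.6 | 85–90% | 91–99% |
| 4.9 | 92–95% | 95–100% |

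- The false rise is about 3 to 28 points. It appears even at assessor SD 0, because chance differences between assessor means are enough.
- Wider grid (GP and GP-by-modality SD 0.2–0.6, item SD 0.3–0.9, assessor SD 0 and 0.4, means 3.4–4.6): 0.5 to 42 points.
- Fail-to-pass switches were at most 0.2% at assessor SD up to 0.4, and 1.9% at 0.8.
- Both visits normalised (mean 3.8, assessor SD 0): 57% against 57%, no rise. Both are 83 − 57 = 26 points below the raw figure.
- Total ≥ 21 in place of all-seven (means 3.0–4.9): S3 minus S2 was about −6 to +5 points, so the one-way bias belongs to the all-seven rule. On raw scores at mean 3.4, total ≥ 21 passes 9 to 15 points more than all-seven.

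**Independent check.** With GP and modality SD 0.35, item SD 0.5, assessor SD 0–0.4, means 3.0–4.3 and 3000 runs per setting, the false rise was about 12 to 31 points. At mean 3.5 and assessor SD 0.2, normalised S2 was 39.7% and raw S3 70.1%; raw S2 was also 70.1%. With three GPs per assessor (15 GPs, close to the expected 16) the same setting gave 39.4% against 70.1%.

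**The case against.** The strongest reply is that S3 is shorthand. SAP 5.2 defines an outcome in full at three months and briefly at six: S5 omits the response options listed under S4, and S3 omits the rationale for the cut. On that reading S3 inherits the normalisation and the time artefact disappears. This is a possible reading, but neither document says so, and it leaves both proportions biased down.

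A second reply is that the text rescales an assessor's score, which could mean the modality total, and a rescaled total against 21 shows no one-way bias. However, the stated rule is all seven domains, which requires item scores. The 21 may also be simple multiplication and not a second pass mark, which is a fair point.

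Third, the size is unknown. With smaller SDs (GP and GP-by-modality 0.2, item 0.3, assessor 0.2) the gap was about 5 points at mean 4.2 and under 1 at 4.6. With equal assessor means it is nil. This stands: the direction is secure and the size is not.

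Fourth, dropping a prespecified adjustment once analysis has begun moves S2 in the favourable direction, and the balance of raw scores over time assumes that each assessor's severity is stable. Both points stand, which is why the prespecified result must remain visible.

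Finally, these are descriptive secondary proportions and no S2–S3 test is planned. That limits the consequence but does not remove it.

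**Conclusion.** The concern holds and should be fixed. On the text of both documents, S2 and S3 follow different rules and are not comparable as written. With the protocol's mean-based factor, whole-number items and the all-seven cut, the rescaling lowers S2 unless an assessor's mean is at or below two-thirds of the average. That direction is arithmetic.

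The size rests on assumed score distributions: roughly 3 to 28 points in the base setting and 0.5 to 42 in the wider grid. It is largest when many items score exactly 3 and near zero when almost none do. The SAP's printed formula gives no usable result. The primary outcomes P1 and P2 and the S6 comparison state no normalisation and are untouched.

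**What to change.** Compute S2 and S3 by one rule on raw item scores, all seven items at least 3, at both visits, and delete the multiplicative normalisation from this thresholded outcome. Under SAP 7 each assessor rates the same number of participants at both visits, so the raw comparison over time is already balanced for assessor if severity is stable. If severity is to be examined, use the continuous total score with an assessor term, at both visits, as a sensitivity analysis.

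Restore the all-seven condition for S3 in Protocol 2b, and reconcile the four and five assessors in Protocol 12. Say whether 21 of 35 is only arithmetic; if it is kept as a pass mark, label it supplementary and report it at both visits.

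The cost is wording in SAP 5.2 and Protocol 2b and 12, with no new data. S2 would lose its assessor adjustment, as is already the case for P1, P2 and S6. SAP 13 records that "During the data analysis it was decided to drop the additional outcome S7", so analysis was under way when the SAP was last amended. Report this change as a dated post hoc amendment, and show S2 under the prespecified rule (mean-based factor) next to the raw result.
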